However, current ADHF management paradigms do not account for or address the marked physical dysfunction in hospitalized older patients with acute HF.(3;4;50) This may also explain why trials of a wide range of interventions in ADHF have been largely negative(6-8;11;12;12) and disease management programs have had, at most, modest impact on long-term outcomes and mortality.(6;37;68;69)

Furthermore, the exercise training trials in HF to date (n >17) have systematically excluded ADHF patients in this key period of vulnerability.(70-73) The largest of these, the NIH-funded HF-ACTION trial, systematically excluded patients with ADHF and those within 6 weeks of hospital discharge.(73;74) Possibly because of recent instability, the study did not significantly reduce the primary endpoint of all-cause mortality or all-cause hospitalizations.(74) HF-ACTION also enrolled relatively few older patients, excluded those with multiple comorbidities, and utilized a traditional cardiac rehabilitation exercise training intervention that would not have been appropriate for older patients with significant frailty. As a result, and similar to prior trials, it likely missed the patients who are elderly, frail, and have multimorbidity who have the largest potential for improvements in outcomes.(3;3;4;75-77)

Prior exercise training studies in HF have not addressed the domains of balance and strength which are important for preventing early injuries in frail, older hospitalized ADHF patients (78) and for enhancing gains in function.(79) Prior intervention studies in older hospitalized patients that have included these domains have generally excluded patients with HF. (65;67;78-80) However, the results of such studies informed and support the primary hypothesis of the proposed study.(41;79-82) For instance, Morris et al showed that an early mobility program improved outcomes in older hospitalized patients with acute respiratory failure.(82) In a non-randomized quasiexperimental study, Tinetti et al. recently showed that a restorative home care model that included physical function reduced rehospitalizations by one-third in older patients, some of whom had HF.(41) The primary hypothesis is also supported by our pilot study which showed that in older patients with ADHF, the proposed intervention can improve SPPB score, a strong predictor of hospitalization, disability, and death.(38)

4. Overview of Investigational Plan

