6.3 Randomization

Once a participant has been identified who satisfies all enrollment criteria, informed consent has been obtained, and baseline testing is complete, the participant will be randomized to a multi-domain rehabilitation intervention group or to an attention control group. Block randomization will be performed, stratified on clinical center and ejection fraction (<45, ≥45), and will be performed by a centralized, web-based system developed and maintained by [name].

7. Investigational Intervention

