10.1.1 SPPB

The SPPB was chosen as the primary outcome because: 1) physical function is an independently important outcome in older persons; 2) the SPPB is a well-accepted, reliable. validated measure of physical function in the older population, (89) and is safe and feasible in clinic, home, and hospital settings, (90) including hospitalized older ADHF patients HF; (28;29;37) 3) the SPPB score is highly predictive of important clinical outcomes, including disability, hospitalization, nursing home admission, and death; (89;91-94) 4) it is sensitive to change in health status(95) and responsive to exercise training;(65;67;96;97) 5) interventions that improve SPPB also improve clinical events, providing independent confirmation of validity; (98;99) 6) the SPPB is a key outcome in LIFE, the largest NIA-funded physical function intervention trial; 7) in our pilot study, the improvement in SPPB explained 90% of the improvement in rehospitalizations, providing a mechanistic link; and 8) the SPPB is standardized, simple, and relatively brief (<10 minutes). The SPPB measures physical function using 3 components: usual gait speed over 4 meters, time to complete 5 chair rises, and standing balance with progressively narrow base of support. Each component is scored on a 0-4 scale and summed for an overall score range of 0-12. Each component of the SPPB is independently associated with important outcomes including mortality.(100:100) Gait speed is associated with survival at increments of 0.1 m/s in community-dwelling adults(101) and is associated with survival in hospitalized older adults with coronary disease.(102)

10.1.2 6MWD

The 6MWD test is a well-established outcome measure in HF. It is valid and reproducible in patients with a wide range of physical function, predicts clinical events, and responds to interventions.(103-106) We showed that it is as predictive of clinical events as exercise oxygen consumption,(107) and improves with exercise training including in older HF patients.(74;108) Although most studies involved outpatients with stable HF, the 6MWD is safe, feasible and

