14.1 Statistical Methods

The primary aim of the study is to assess the efficacy of the REHAB-HF intervention on physical function measured by the total SPPB score. The effect of the intervention on SPPB score measured 3 months post-randomization will be estimated and tested for significance using analysis of covariance, where the randomized arm is the between-subject grouping variable and the pre-randomized measure of SPPB score, clinical site, age, gender, and ejection fraction category (preserved vs. reduced) will be covariates. Least square means will be used to estimate the intervention effect. Tests will be conducted at the 5% two-sided level of significance.

The secondary aim of the study is to assess the intervention's effect on the total number of all-cause rehospitalizations during the 6 months following discharge from the index hospitalization. Since the count of all-cause rehospitalizations per participant may not be normally distributed, the effect of the intervention on total all-cause rehospitalizations will be estimated using a Poisson model for modeling count data, where the randomized arm is the between-subject grouping variable and clinical site, age, gender, and ejection fraction category will be covariates. A supplemental analysis will be performed adding the duration of the index hospitalization and the number of inpatient intervention sessions as additional covariates.

The proportion of the intervention's effect on total all-cause rehospitalizations that can be explained by its effect on 3-month SPPB score will be analyzed by multivariable regression between total number of all-cause rehospitalizations and the residual of the analysis of covariance model for 3-month SPPB omitting intervention from the model.

Similar statistical methods as described above will be used for all of the exploratory efficacy parameters.

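### The rehospitalization model in section 14.1 omits baseline SPPB, a predictor that is already collected; adding it, with a variance that allows for overdispersion, is a modest and nearly free improvement.

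*Combined protocol and SAP*

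**What the plan says.** Section 14.1 gives the covariates of two models in consecutive paragraphs. In the primary ANCOVA, "the pre-randomized measure of SPPB score, clinical site, age, gender, and ejection fraction category (preserved vs. reduced) will be covariates". Rehospitalizations are estimated "using a Poisson model for modeling count data", and there "clinical site, age, gender, and ejection fraction category will be covariates". The second list is the first without baseline SPPB, and no reason is given. No scale parameter, robust variance or negative binomial alternative is mentioned.

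A supplemental rehospitalization analysis is planned, "adding the duration of the index hospitalization and the number of inpatient intervention sessions as additional covariates". It does not add baseline SPPB either.

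Elsewhere the protocol treats SPPB as prognostic for this outcome. Section 3 (Background) says that "the proposed intervention can improve SPPB score, a strong predictor of hospitalization, disability, and death", and section 10.1.1 says that "the SPPB score is highly predictive of important clinical outcomes, including disability, hospitalization, nursing home admission, and death". Under section 6.3, once "informed consent has been obtained, and baseline testing is complete, the participant will be randomized", so the value should exist for everyone randomized. The same section stratifies on clinical center and ejection fraction only.

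**The concern.** A baseline measure that predicts the outcome, is complete before randomization and is not balanced by design is the usual candidate for covariate adjustment. Leaving it out keeps explainable patient-level risk in the sampling variance of the treatment effect. It also means that a chance difference in baseline function between the arms passes straight into the estimated rate ratio.

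The supplemental analysis does not fill the gap. Its two added quantities are settled only by discharge, and study sessions in hospital are given only in the intervention arm (sections 7.1 and 7.2.1).

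The rehospitalization aim sets the trial's size: section 14.2 needs 334 evaluable participants for it and 258 for the primary aim. It is planned at 80% power with a small margin from rounding up, so an inexpensive gain is worth having.

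**Working it through.** **Inputs from section 14.2.** 80% power; a 25% reduction, equal to 0.41 absolute; 334 evaluable; up to 5% inevaluable; 352 required, rounded up to 360. The 5% two-sided level is stated in section 14.1 for the primary aim and is assumed to apply here.

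**The plan's own figure.** 334/0.95 = 351.6, so 352 reproduces. The 334 cannot be checked directly, because no SD is stated and the ± values beside the pilot means are not labelled. It can be solved backwards:
- Control mean 0.41/0.25 = 1.64; intervention mean 1.64 − 0.41 = 1.23; average 1.435.
- With pure Poisson variance, n per arm = (1.64 + 1.23) × (1.960 + 0.842)² / 0.41² = 134, or 268 in total.
- 334/268 = 1.25, the implied dispersion φ. Starting from the pilot control mean of 1.673 gives 1.27. (The pilot means imply a 30.8% reduction, since 1 − 1.157/1.673 = 0.308, against the stated 29.3%. This does not change the conclusion here.)

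**Assumed input.** The documents give no rate ratio per SD of SPPB. The range used is 0.90, 0.85, 0.80 and 0.75.

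**True precision.** Share of outcome variance removed: R² = 1.435 × (exp(ln(RR)²) − 1)/1.25. Evaluable participants: 0.95 × 360 = 342. Power = Φ(2.802 × √(342/(334 × (1 − R²))) − 1.960), which is 80.9% at R² = 0.

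| RR per SD | R² | Power | Gain (points) |
|---|---|---|---|
| 0.90 | 1.3% | 81.4% | 0.5 |
| 0.85 | 3.1% | 82.1% | 1.2 |
| 0.80 | 5.9% | 83.2% | 2.3 |
| 0.75 | 9.9% | 84.8% | 3.8 |

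A simulation with 342 evaluable, dispersion 1.25, robust standard errors and 1,500 trials per setting gave 81.2 to 81.8% at 0.90, 82.0 to 83.6% at 0.80 and 81.3 to 85.1% at 0.75. These are gains of 0.6, 1.6 and 3.8 points.

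**What a plain Poisson fit would report.** With 171 per arm, expected events are 171 × 1.64 = 280 and 171 × 1.23 = 210. The model-based SE of the log rate ratio is √(1/280 + 1/210) = 0.091. It depends on event counts, and in simulation it was 0.091 both with and without the covariate. At dispersion 1.25 the true SE is about 0.091 × √1.25 = 0.102, so the plain test is too liberal. Its type I error is 2Φ(−1.96/√1.25) = 8.0%. Replacing 1.25 by 1.25 × (1 − R²) gives 7.8% at 0.90, 7.1% at 0.80 and 6.5% at 0.75. The simulation at dispersion 1.25 showed the same direction: 9.2 to 9.0%, 8.5 to 7.3% and 8.3 to 5.9%.

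**Chance imbalance.** The SE of the baseline difference between arms is √(4/342) = 0.108 SD. One SE shifts the log rate ratio by 0.108 × 0.105 = 0.011 at 0.90 and by 0.108 × 0.288 = 0.031 at 0.75. Relative to the design effect |ln 0.75| = 0.288, that is 4% to 11%. At a 95% imbalance (1.96 × 0.108 = 0.21 SD) the rate ratio moves by a factor of exp(0.21 × 0.105) = 1.02 to exp(0.21 × 0.288) = 1.06.

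**The case against.** The strongest reply is that the adjustment would change nothing visible. A Poisson model with no scale term reports the same standard error whether or not SPPB is in it. This stands: the printed interval narrows only if the variance method changes too. The unaddressed overdispersion is the larger weakness of this model.

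Second, the size is assumed, and the range leans high. The variance-share formula credits SPPB with all of its association, but part of that may already be carried by age, gender, site and ejection fraction. At dispersion 1.25 the excess variance is 0.25/1.25 = 20% of the total, so the 9.9% case has SPPB alone explaining about half of it. This also stands, and it is why the result is given as an upper range.

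Third, imbalance of this kind is ordinary sampling variation. Even one SE at the 0.75 extreme (0.031) is about a third of the standard error. This is correct, and it limits the claim to a small one.

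Fourth, choosing SPPB could be called a preference, since the protocol also describes the 6-minute walk (10.1.2), KCCQ (10.2.1) and frailty (10.7) as prognostic, and the existing set already holds both stratification factors plus age and gender. That set is defensible. But SPPB is the one such measure that the plan already adjusts for in the primary analysis, so adding it is not an arbitrary selection.

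A sponsor might also say that adjustment changes what is estimated. With a log link, randomization and no arm-by-SPPB interaction, the rate ratio is collapsible, so the target is unchanged.

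**Conclusion.** The point holds as an efficiency and robustness improvement. Adding baseline SPPB would yield roughly 0.5 to 4 power points for the rehospitalization aim and would correct shifts of about 0.01 to 0.03 in the log rate ratio per SE of imbalance. This rests on assumed rate ratios of 0.90 to 0.75 per SD, a dispersion back-solved from the 334, no overlap with the existing covariates, and a variance method that can register the gain. If the association is weak, the benefit is near zero, and so is the cost.

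Four stronger readings are tempting, and the documents do not support them:
- A reader might infer that the omission biases or invalidates the analysis. It does not; the arms are randomized.
- A reader might infer that adding SPPB alone would narrow the reported interval. Under a dispersion fixed at 1 it would not.
- A reader might turn the gain into a number of participants saved. The documents give neither the strength of association nor the dispersion needed for that.
- A reader might infer a covariate mismatch with the analysis of how much of the effect SPPB explains. That analysis uses the residual of a 3-month SPPB model that already contains baseline SPPB, so the residual is uncorrelated with it by construction. Section 14.1 lists no other covariates for that regression, so no mismatch is shown.

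**What to change.** In section 14.1, add baseline SPPB to the pre-specified covariates of the rehospitalization model. Do the same in the count models for the exploratory rehospitalization endpoints (section 12.3). In the same edit, state a variance that allows for overdispersion: robust, scale-adjusted Poisson or negative binomial. Make the change before any unblinded look at outcomes, so that it cannot appear data-driven.

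The cost is one degree of freedom and a change of variance method. No new data are needed, and no participants should be lost, because baseline testing is completed before randomization.

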7.1 Attention Control

Participants randomized to the attention control arm will be notified immediately, and will follow standard care as ordered by their individual, treating physician. Importantly, to reduce the potential for bias from greater attention and surveillance in the rehabilitation intervention group, participants in the attention control group will receive at least bi-weekly contact from study personnel during the first 3 months following the index hospitalization. This contact will be provided as a combination of telephone calls and specified study visits. Specifically, contact will be made with study visits at weeks 4 and 12 and with telephone calls at weeks 2, 6, 8, and 10. Further, in-person contact will be made within the first 2 weeks following discharge for the purposes of retention (section 8.2.2). Consistent with the rehabilitation intervention group, telephone contact will also be made at weeks 14, 16, 20, and 24. Information regarding symptoms, HF transitional management program use, medical compliance, activity level, rehabilitation received, medical resource utilization, and clinical events will be collected at each of these encounters.

Participants in the attention control arm will not receive any specific rehabilitation recommendations or exercise prescription from study personnel. They may, however, receive any physical or occupational therapy deemed appropriate by their usual clinical care providers, both during the hospitalization and as outpatients.

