7.2 Rehabilitation Intervention Group

7.2.1 REHAB-HF Rehabilitation Intervention Overview

The multi-domain rehabilitation intervention for this study is a novel integration of rehabilitation therapies developed specifically for older heart failure patients who have been hospitalized for ADHF; a population characterized by heterogeneity in mobility status, multiple co-morbid conditions, and high rates of frailty.(48;50;83-85) The goal of the intervention is to increase endurance, mobility, strength, and balance utilizing reproducible targeted exercises administered by a multi-disciplinary team with specific milestones for progression.

This is a transitional intervention which begins during the acute hospitalization and continues for 12 weeks after discharge in the outpatient setting. The intervention will be administered once daily in the hospital and 3 days per week in the outpatient setting. Each session will include 3 stages: 1) warm-up (seated core exercises, 2-3 minutes light walking if able, and stretching exercises), 2) rehabilitation/training, and 3) cool-down (stretching exercises). The rehabilitation/training portion of each session will include exercises tailored based on participant performance in each of 4 domains: endurance, mobility, strength, and balance.

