7.2.2 Initiation of the Rehabilitation Intervention

Participants randomized to the multi-domain rehabilitation intervention will begin the intervention in the hospital as soon as possible after randomization. Though not required for enrollment, when possible the intervention will begin in the hospital. Plans for the initiation / continuation of the intervention in the outpatient setting will be made prior to hospital discharge and will be scheduled to begin within the first week following discharge.

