7.2.4 Exercise Duration

During the hospitalization, each rehabilitation session will last for approximately 45 minutes and will include warm-up (~5 minutes), cool-down (~5 minutes), and rest periods as needed. The outpatient rehabilitation sessions will last for approximately 60 minutes (range 45 - 75 minutes), including 5 to 10 minutes each for warm-up and cool-down periods. The relative time spent on each domain during the rehabilitation session will be tailored to the participant's physical function impairments. Specifically, a participant with poor balance and functional mobility will spend a greater proportion of time performing balance and mobility exercises in the early portions of the intervention. As balance and functional mobility improve, these will comprise a smaller portion of the session and time spent on endurance will be increased. Alternatively, a participant with only modest impairments in balance and functional mobility at baseline will spend most of the exercise session performing endurance and strengthening exercises, even early in the intervention.

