7.3 Intercurrent Illness and Interruption to Study Intervention

Interruptions to the study intervention, including illness and hospitalization, are anticipated. Although this is an intention-to-treat protocol, to help ensure each participant has a reasonable opportunity to complete the study intervention (defined as completing at least 30 outpatient sessions) and that the physical performance outcome measures reflect the intended intervention of this study, limited extensions of the study intervention are included in the study protocol. Participants who suffer an illness, hospitalization or other complications that interferes with participating in the study intervention will resume the intervention once medically stable. Participants will have up to 4 additional weeks beyond the initially planned 12 weeks to attempt to complete the multi-domain intervention.

In addition, if a participant is acutely ill or hospitalized within 2 weeks of the anticipated date of the final 3-month visit, the visit will be delayed for up to 2 weeks to allow for up to 6 additional rehabilitation and exercise sessions. Similarly, the final 3-month visit for those in the attention control arm will also be delayed for up to 2 weeks in the event of acute illness or hospitalization within 2 weeks of the date of the visit.

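### The supplemental rehospitalization model adjusts for inpatient intervention sessions, which are part of the treatment, so its arm term does not estimate the intervention effect

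*Combined protocol and SAP*

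**What the plan says.** Section 14.1 estimates the intervention effect on 6-month all-cause rehospitalizations with a Poisson model "where the randomized arm is the between-subject grouping variable and clinical site, age, gender, and ejection fraction category will be covariates". It then states: "A supplemental analysis will be performed adding the duration of the index hospitalization and the number of inpatient intervention sessions as additional covariates". Because these terms are added, arm remains in the model. The plan gives no purpose for the supplemental model, no coding rule for sessions in controls, no centring and no interpretation of the arm term.

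Other sections show what the session count is:

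- Section 7.2.1: "The intervention will be administered once daily in the hospital and 3 days per week in the outpatient setting". The outpatient part "continues for 12 weeks after discharge in the outpatient setting". Inpatient sessions are thus one component of the assigned treatment.
- Section 7.2.2: the intervention starts after randomization, and an inpatient start is expected but not mandatory: "Though not required for enrollment, when possible the intervention will begin in the hospital".
- Section 7.1: controls "will not receive any specific rehabilitation recommendations or exercise prescription from study personnel". Their count is zero by design, although the plan does not say so.

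**The concern.** A covariate in a treatment comparison should be fixed before randomization. Inpatient session count is not: it is a consequence of assignment and a part of what was assigned. Conditioning on it removes from the arm term whatever the inpatient sessions contribute, and brings in any association between session count and prognosis within the intervention arm.

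Such an association is plausible from the protocol itself. Daily delivery ties the count to length of stay. Section 7.2.8 stops sessions for abnormal vital signs or symptoms. Section 7.2.12 lets physician-ordered care take precedence. Section 7.2.2 allows no inpatient start at all.

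What is at stake is how one prespecified result is read. The sentence sits in the paragraph on the intervention's effect and calls sessions a covariate, so the arm term could be reported as an adjusted intervention effect. If it then differs from the main model, or loses significance through collinearity alone, the main finding could wrongly look fragile.

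Total index stay is a lesser instance of the same problem, because randomization occurs during the stay and the total includes days after it.

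**Working it through.** The plan gives no figure for this model, so there is none to reproduce.

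**1. What the arm term estimates.** Write the model as

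log E[Y] = a + bA·Arm + bS·Sessions + bL·Stay + other covariates, with Sessions = 0 for all controls.

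At s sessions the rate ratio between arms is exp(bA + bS·s), so exp(bA) is the contrast at s = 0. It equals the intervention effect only if bS = 0. Controls have no variation in sessions, so bS comes from the intervention arm alone. Subtracting one constant c from everyone's count changes only the intercept, so ordinary centring does not help. If controls were coded missing, they would drop out and the arm term could not be estimated.

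**2. Inputs for size.**

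- From section 14.2: 360 participants, control mean 1.673, target reduction 25% (rate ratio 0.75).
- From sections 7.2.1 and 7.3: 3 × 12 = 36 planned outpatient sessions; completion is "defined as completing at least 30 outpatient sessions".
- From section 7.2.4: in hospital "each rehabilitation session will last for approximately 45 minutes"; outpatient sessions last about 60 minutes.
- Assumed, because the documents do not give them: a mean of 2 to 3 inpatient sessions, their SD, the in-hospital share of benefit, and any link with prognosis.

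**3. Benefit delivered in hospital.** If benefit is log-linear in sessions and a given share of the log effect is inpatient, the arm term is 0.75^(1 − share).

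| Basis | Share | Arm rate ratio |
|---|---|---|
| 2 of 38 sessions | 5.3% | 0.761 |
| 2 of 32 | 6.3% | 0.764 |
| 3 of 39 | 7.7% | 0.767 |
| 3 of 33 | 9.1% | 0.770 |
| Minutes, lowest: 90/(90 + 2160) | 4.0% | 0.759 |
| Minutes, highest: 135/(135 + 1800) | 7.0% | 0.765 |
| Sensitivity only | 25% | 0.806 |
| Sensitivity only | 50% | 0.866 |

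The documents do not support the last two shares.

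**4. Link with prognosis, all benefit outpatient.** Simulation with 2000 runs per case:

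- 180 per arm, with a dispersion-scaled Poisson fit including site, age, gender and ejection fraction category.
- Gamma-Poisson counts with variance about twice the mean at the control rate.
- An unmeasured severity factor with SD 0.3 on the log rate (rate ratio 1.35 per SD).
- Supplemental fit adding total stay and sessions.

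Arm rate ratios by correlation of severity with sessions (positive means sicker patients get more sessions):

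| Sessions, mean (SD) | −0.4 | −0.2 | +0.2 | +0.4 |
|---|---|---|---|---|
| 2 (1.95) | 0.809 | 0.780 | 0.724 | 0.698 |
| 3 (2) | not run | 0.792 | 0.710 | not run |
| 2 (1) | not run | 0.818 | 0.672 | not run |

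The main model gave 0.750 in each. With no link and no in-hospital share, the supplemental term at mean 2, SD 1.95 was 0.751, as the algebra requires.

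**5. Precision.** Ignoring stay and other covariates, Var(bA) = Var(main) + m²·Var(bS), where m is the mean count. The SE ratio is then √[1 + (m/SD)²/(1 + 0.75)].

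| Sessions, mean (SD) | Formula | Simulated SE ratio |
|---|---|---|
| 2 (1.95) | 1.27 | 1.31-1.35 |
| 3 (2) | 1.51 | 1.61-1.65 |
| 2 (1) | 1.81 | 1.82-1.89 |
| 3 (1) | 2.48 | 2.48-2.50 |

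A separate simulation (control mean 0.41/0.25 = 1.64, 600 runs, no extra between-patient variation, sessions without effect) raised the SE from 0.089 to 0.113, 0.133 and 0.164 at means of 1, 2 and 4 sessions. Power fell from 0.88-0.91 to 0.72, 0.58 and 0.42.

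**6. Replacement model.** Without sessions, and with pre-randomization stay in place of total stay, the simulated rate ratio was 0.743-0.752 with an SE ratio of 1.00 in all cases.

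**The case against.** The strongest reply is that the plan already separates the two analyses. The intervention effect is assigned to the main Poisson model, the second model is called supplemental, section 14.2 powers nothing on it, and the plan never says that its arm term is the intervention effect. This stands as a limit on severity. It does not supply a valid reading of the arm term.

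A second reply concerns parameterization. If sessions are centred at the intervention-arm mean, with controls left at zero, the arm term becomes bA + bS·m, the contrast at average dose. In simulation that version gave 0.74-0.76, the same as the main model, with an SE ratio of 0.99-1.00. This is correct, but it needs an arm-specific centring that the plan does not state.

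Third, the only magnitude tied to protocol figures is small (0.76-0.77 against 0.75), and even that needs an assumed mean session count. The wider ranges rest on an assumed severity factor, correlations and session distributions. This also stands: no material distortion in this trial has been shown. Adjusting for stay in the same model does not remove the prognosis link, because the simulated supplemental model includes it and still shifts.

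Finally, the within-arm dose model carries the same non-randomized information as the present slope. That is true; its advantage is that it does not present that information beside a randomized contrast.

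**Conclusion.** The concern holds. As written, the supplemental arm coefficient is a contrast at zero inpatient sessions. It is not the intervention effect unless sessions are unrelated to outcome given arm and the other covariates. That conclusion is algebraic; it rests on controls counting as zero, which is inferred from the design, and on no arm-specific centring.

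The size is uncertain. The shift is about 0.01 to 0.02 in the rate ratio if in-hospital benefit is proportional to sessions or minutes. Under the assumed prognosis links it can go either way, from 0.67 to 0.82 across the cases run. The loss of precision does not need any bias: it appears in every case examined.

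The consequence is confined to this one result. The primary ANCOVA, the main secondary model and the sample size do not depend on it. Severity is minor to moderate: the sentence should be changed, but the trial's main conclusions are not at risk.

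**What to change.** In section 14.1, remove the number of inpatient intervention sessions from the between-arm supplemental model. If session dose is of interest, add a model of rehospitalizations on inpatient sessions within the intervention arm only, adjusted for stay length and labelled as a non-randomized description.

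Optionally, if stay length is kept in the between-arm model, use days from admission to randomization, which is a baseline value, in place of total index stay.

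The cost is one sentence. Admission and randomization dates are routine trial data. The between-arm model would no longer yield a session coefficient; the within-arm model supplies it.
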